  - d. Have any medical or surgical condition, which in the opinion of the investigator would put the participant at increased risk from participating in the study
  - e. Persons directly involved in the conduct of the study
15. Previous or current treatment (within 90 days of screening) with monoclonal antibodies directed towards PCSK9, or with inclisiran or ezetimibe.

16. Active liver disease defined as any known current infectious, neoplastic, or metabolic pathology of the liver or alanine aminotransferase (ALT) elevation >3x ULN, aspartate aminotransferase (AST) elevation >3x ULN, or total bilirubin elevation >2x ULN (except patients with Gilbert's syndrome) at screening confirmed by a repeat measurement at least one week apart.

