## **6.5.2 Follow-up for toxicities**

### **6.5.2.1 Follow up on potential drug-induced liver injury (DILI) cases**

Participants with transaminase increase combined with total bilirubin increase may be indicative of potentially severe DILI, and should be considered as clinically important events and assessed appropriately to establish the diagnosis. The required clinical information, as detailed below, should be sought to obtain the medical diagnosis of the most likely cause of the observed laboratory abnormalities.

The threshold for potential DILI may depend on the participant's baseline AST/ALT and total bilirubin value; participants meeting any of the following criteria will require further follow-up as outlined below:

- For participants with normal ALT and AST and total bilirubin value at baseline: AST or ALT  $> 3.0 \times$  ULN combined with total bilirubin  $> 2.0 \times$  ULN
- For participants with elevated AST or ALT or total bilirubin value at baseline: [AST or ALT  $> 2 \times$  baseline] OR [AST or ALT  $> 300$  U/L] whichever occurs first combined with [total bilirubin  $> 2 \times$  baseline AND  $> 2.0 \times$  ULN]

A detailed history, including relevant information such as review of ethanol consumption, concomitant medications, herbal remedies, supplement consumption, history of any pre-existing liver conditions or risk factors, should be collected.

Laboratory tests should include ALT, AST, total bilirubin, direct and indirect bilirubin, gamma-glutamyl transferase (GGT), glutamate dehydrogenase (GLDH), prothrombin time (PT)/International Normalized Ratio (INR), alkaline phosphatase (ALP), albumin, and CPK.

Perform relevant examinations (Ultrasound or Magnetic resonance imaging (MRI), Endoscopic retrograde cholangiopancreatography (ERCP)) as appropriate, to rule out an extrahepatic cause of cholestasis. Cholestasis (is defined as an ALP elevation  $> 2.0 \times$  ULN with R value  $< 2$  in

participants without bone metastasis, or elevation of the liver-specific ALP isoenzyme in participants with bone metastasis).

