**Table 16-4 Follow up requirements for liver laboratory triggers with liver symptoms**

ALT or AST	TBL	Liver Symptoms	Action
ALT or AST increase without bilirubin increase:			
If normal at baseline: ALT or AST > 3 x ULN  If elevated at baseline: ALT or AST > 2 x baseline or > 300 U/L (whichever occurs first)	Normal For patients with Gilbert's syndrome: No change in baseline TBL	None	
 
• No change to study treatment
 
• Measure ALT, AST, ALP, GGT, TBL, direct and indirect bilirubin, PT/INR, albumin, CPK, and GLDH in 48-72 hours.
 
• Follow-up for symptoms.
 

ALT or AST	TBL	Liver Symptoms	Action
If normal at baseline: ALT or AST > 5 x ULN for more than two weeks  If elevated at baseline: ALT or AST > 3 x baseline or > 300 U/L (whichever occurs first) for more than two weeks	Normal  For patients with Gilbert's syndrome: No change in baseline TBL	None	
 
• Interrupt study drug
 
1. Measure ALT, AST, ALP, GGT, TBL, direct and indirect bilirubin, PT/INR, albumin, CPK, and GLDH in 48-72 hours.
 
• Follow-up for symptoms.
 
• Initiate close monitoring and workup for competing etiologies.
 
• Study drug can be restarted only if another etiology is identified and liver enzymes return to baseline.
 

If normal at baseline: ALT or AST > 8 x ULN	Normal	None	
ALT or AST increase with bilirubin increase:			
If normal at baseline: ALT or AST > 3 x ULN  If elevated at baseline: ALT or AST > 2 x baseline or > 300 U/L (whichever occurs first)	TBL > 2 x ULN (or INR > 1.5)  For patients with Gilbert's syndrome: Doubling of direct bilirubin	None	
If normal at baseline: ALT or AST > 3 x ULN  If elevated at baseline: ALT or AST > 2 x baseline or > 300 U/L (whichever occurs first)	Normal or elevated	Severe fatigue, nausea, vomiting, right upper quadrant pain	

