The number and percentage of participants satisfying Hy's Law will also be tabulated by treatment group based on the following lab findings:

- Any elevated post-baseline aminotransferases defined as:
 - ALT > 3 x ULN or
 - AST > 3 x ULN
- Elevated post-baseline serum total bilirubin (TBL) > 2 x ULN and serum alkaline phosphatase (ALP) levels < 2 x ULN

Participants must meet all of the criteria listed above at the same time point and have normal lab variables (ALT, AST, TBL) at baseline to be considered a Hy's Law case. The same analysis will be performed excluding the normal baseline value requirement.

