5.2 Laboratory parameters derivations**5.2.1 Handling data with special symbols**

Any laboratory parameters with values identified as $<x$, $\leq x$, $>x$, or $\geq x$ will be analyzed using the 'x' value (the analysis will ignore the $<$, \leq , $>$, or \geq symbol).

5.2.2 Criteria for Potentially Clinically Significant and Clinically Significant abnormal laboratory tests

criteria are explicitly stated in the table below. For all other parameters, a PCS/CS criterion is met when both of the following occur:

- There is a post-baseline value that meets the threshold
- The baseline value does not meet the threshold

Some examples are:

- For leukocytes, a subject satisfies " $\leq 2.8 \times 10^9/L$ " criterion as long as the baseline value is $> 2.8 \times 10^9/L$ and any post-baseline value is $\leq 2.8 \times 10^9/L$; a subject satisfies " $\geq 16 \times 10^9/L$ " criterion as long as the baseline value is $< 16 \times 10^9/L$ and any post-baseline value is $\geq 16 \times 10^9/L$.
- For CK, a subject satisfies " > 3 and $\leq 5 \times ULN$ " criterion as long as the baseline value is $\leq 3 \times ULN$ and any post-baseline value is > 3 and $\leq 5 \times ULN$. A subject satisfies " > 5 and $\leq 10 \times ULN$ " criterion as long as the baseline value is $\leq 5 \times ULN$ and any post-baseline value is > 5 and $\leq 10 \times ULN$. If a subject satisfies both " > 3 and $\leq 5 \times ULN$ " and " > 5 and $\leq 10 \times ULN$ " criteria and does not satisfy the criteria of any more severe category, the subject will be presented under " > 5 and $\leq 10 \times ULN$ " but not under " > 3 and $\leq 5 \times ULN$ " because the most severe category will be used for CK.
- For serum creatinine, the CS criterion is satisfied if at least one of the following is true:
 - The baseline value is ≤ 2 mg/dL and any post-baseline value is > 2 mg/dL.
 - Any post-baseline value is $\geq 50\%$ increase from baseline, regardless of whether the baseline value is ≤ 2 mg/dL.

Variable	Unit	Lower Boundary	Upper Boundary
Hematology			
Hematocrit	%	$\leq 0.8 \times LLN$	N/A

Variable	Unit	Lower Boundary	Upper Boundary
Hemoglobin	g/dL	≤10 g/dL	N/A
Platelet Count	10 ⁹ /L	≤75*	≥700*
White Blood Cell Count	10 ⁹ /L	≤2.8	≥16
Serum Chemistry			
Alanine Aminotransferase (ALT/SGPT)	U/L	N/A	>1 and ≤3 × ULN
Alanine Aminotransferase (ALT/SGPT)	U/L	N/A	>3 and ≤5 × ULN*
Alanine Aminotransferase (ALT/SGPT)	U/L	N/A	>5 and ≤10 × ULN*

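### The repeat Hy's Law table keeps fixed ULN cut-offs for participants with abnormal baseline liver tests, for whom the protocol uses baseline-relative criteria

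*SAP*

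**What the plan says.** **SAP 2.7.3.** A Hy's Law case needs ALT or AST above 3 x ULN together with "Elevated post-baseline serum total bilirubin (TBL) > 2 x ULN and serum alkaline phosphatase (ALP) levels < 2 x ULN", all at the same time point. Participants must also "have normal lab variables (ALT, AST, TBL) at baseline to be considered a Hy's Law case". The table is then repeated: "The same analysis will be performed excluding the normal baseline value requirement". Nothing else changes in the repeat.

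**Protocol 6.5.2.1 (potential drug-induced liver injury).** The fixed cut-offs apply when ALT, AST and bilirubin are all normal at baseline. A second rule begins "For participants with elevated AST or ALT or total bilirubin value at baseline". It requires AST or ALT above 2 x baseline or above 300 U/L, combined with total bilirubin above both 2 x baseline and 2 x ULN. It has no ALP condition.

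**Protocol Appendix 2.** Table 16-3 gives its fixed-ULN definition of potential Hy's Law cases under the normal-baseline heading. For raised baseline aminotransferases, Table 16-4 uses "ALT or AST > 2 x baseline or > 300 U/L (whichever occurs first"). For Gilbert's syndrome, in the rows with a bilirubin increase, it uses a doubling of direct bilirubin.

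**Who can be enrolled.** Exclusion 16 removes only confirmed ALT or AST above 3 x ULN. Its bilirubin limit of 2 x ULN applies "except patients with Gilbert's syndrome".

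**SAP 5.2.2.** A CS laboratory criterion needs a post-baseline value that meets the threshold and the condition "The baseline value does not meet the threshold". The bilirubin threshold is above 2 x ULN. Creatinine also has a rule for a 50% rise from baseline.

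**The concern.** The repeat table can add only participants whose baseline ALT, AST or bilirubin was not normal. For them a fixed multiple of ULN does not separate a new rise from a long-standing value. If bilirubin was already above 2 x ULN, the bilirubin condition is met before treatment starts. If ALT was mildly raised, it can more than double and still stay under 3 x ULN.

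At stake is the agreement between the liver-safety tables and the criteria the protocol gives investigators for the same participants. A count in the repeat table could include unchanged bilirubin, and an empty table would not show that nobody met the protocol criteria.

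**Working it through.** The plan states no figure to reproduce, so the two rules are set side by side. All values are multiples of ULN. Let a0 and a be ALT (or AST) at baseline and on treatment, b0 and b total bilirubin likewise, and p on-treatment ALP.

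- SAP repeat: a > 3, b > 2 and p < 2 at the same time point.
- Protocol 6.5.2.1, abnormal baseline: (a > 2 x a0, or above 300 U/L) and (b > 2 x b0 and b > 2).

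**The 300 U/L alternative.** The documents give no ULN in U/L. If it lies between 30 and 50 U/L (assumption), 300 U/L is 300/30 = 10 down to 300/50 = 6 x ULN. For a0 up to 3, 2 x a0 is at most 6, so the 300 U/L limit is never the lower of the two.

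**Aminotransferase crossover.** 2 x a0 = 3 gives a0 = 1.5. With a0 between 1 and 1.5, rises above 2 x a0 but not above 3 meet the protocol's condition and not the SAP's (a0 = 1.2: above 2.4, up to 3). With a0 above 1.5, values above 3 but not above 2 x a0 meet only the SAP's (a0 = 2.0: above 3, up to 4).

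**Bilirubin.** The protocol also requires b > 2, so the SAP bilirubin cut-off alone never misses a protocol case. With b0 = 2.2, the SAP condition is met with no change, while 6.5.2.1 needs b > 2 x 2.2 = 4.4.

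**Worked cases** (p < 2 unless stated; the other aminotransferase is assumed not to qualify):

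| Case | ALT | Bilirubin | SAP repeat | 6.5.2.1 |
|---|---|---|---|---|
| A. Gilbert's, bilirubin stable | 0.8 to 3.5 | 2.2 to 2.2 | yes | no |
| B. As A, no ALT rise | 0.8 to 0.8 | 2.2 to 2.2 | no | no |
| C. Mildly raised baseline ALT | 1.2 to 2.8 (2.33-fold) | 0.6 to 2.2 (3.67-fold) | no | yes |
| D. As C, larger ALT rise | 1.2 to 3.5 | 0.8 to 2.5 | yes | yes |
| E. As D, ALP 2.3 | 1.2 to 3.5 | 0.8 to 2.5 | no | yes |
| F. Higher baseline ALT | 2.0 to 3.9 (1.95-fold) | 0.8 to 2.5 | yes | no |
| G. Only bilirubin raised at baseline | 0.4 to 0.9 (2.25-fold) | 1.1 to 2.3 (2.09-fold) | no | yes |

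None of these is in the main table, because each has an abnormal baseline value.

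**What the CS summary in 5.2.2 adds.** In case C bilirubin goes from 0.6 to 2.2, so it is counted and listed as CS. The ALT rise is not: 1.2 and 2.8 fall in the same band (above 1, up to 3 x ULN), which the baseline already met. If baseline bilirubin is 2.2, no later value can qualify, because the baseline already meets the threshold; 4.5 x ULN, more than double, would not count. The opening of 5.2.2 is cut off in the text available. I apply the general rule to bilirubin because its table row gives only the cut-off.

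**Data.** AST, ALT, ALP and total bilirubin are in both the full and the limited panel (Protocol 8.4.1.3), so 6.5.2.1 can be evaluated at every scheduled visit. Direct bilirubin is only in the full panel (Days 0 and 330), so the Table 16-4 Gilbert's rule cannot be applied to scheduled samples at Days 90, 180 and 270.

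**The case against.** The strongest reply is that 6.5.2.1 triggers follow-up and is not a tabulation rule. Protocol 12.5.2 plans no Hy's Law table, and the SAP's main table uses the same numerical cut-offs and the same normal-baseline population as Table 16-3. This stands. A reader might infer that the SAP departs from a planned analysis; it does not.

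A reader might also infer that stable Gilbert's bilirubin makes a case by itself. It does not (case B): ALT or AST above 3 x ULN and ALP below 2 x ULN are also needed at the same time point. Comparing the two tables would show which participants the repeat added, though not why.

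Nor are the missed cases lost to the report. Those with baseline bilirubin not above 2 x ULN appear in the CS bilirubin summary. Confirmed cases with no alternative cause are reportable as SAEs under 6.5.2.1, and the SAP has a broad hepatotoxicity search. These last two routes depend on confirmation, attribution and reporting.

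Replacing the fixed rule would do harm. It would drop case F, admit case G, whose ALT is never abnormal, and remove the ALP condition for these participants.

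Defending the repeat as a deliberately broad screen works only in part: it is not broad for case C.

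**Conclusion.** The concern holds in a limited form. For participants with abnormal baseline liver tests, the repeat table can count unchanged bilirubin as half of a Hy's Law case. It leaves out participants with baseline ALT or AST between 1 and 1.5 x ULN who meet 6.5.2.1 without exceeding 3 x ULN. Separately, 5.2.2 cannot register any bilirubin rise from a baseline above 2 x ULN. Reporting is weakest where the last two coincide: such a participant is in neither Hy's Law table and not in the CS bilirubin summary.

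The effect is confined to descriptive liver-safety reporting; no primary endpoint, significance level or sample size is touched. The documents give neither the number of participants with Gilbert's syndrome or raised baseline tests nor an expected number of Hy's Law cases. That few are affected is my judgement. A claim that a single case would change the liver-safety conclusion is therefore not supported.

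The result assumes that the general rule of 5.2.2 covers bilirubin. The two protocol rules for Gilbert's syndrome (total bilirubin in 6.5.2.1, direct bilirubin in Table 16-4) differ and should be reconciled; I take no position on which is clinically right.

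**What to change.** 1. Keep both Hy's Law tables in SAP 2.7.3 unchanged.
2. Add a supplementary row for participants with elevated baseline AST, ALT or total bilirubin, counted by the protocol 6.5.2.1 criteria. State in a footnote that it has no ALP condition, that it uses total rather than direct bilirubin, and whether the conditions must coincide; the same-time-point convention of 2.7.3 is the natural choice.
3. In the repeat table, flag cases whose baseline bilirubin was already above 2 x ULN or who have Gilbert's syndrome in their medical history.
4. In SAP 5.2.2, also count total bilirubin above 2 x baseline as CS when baseline is above 2 x ULN, in the way creatinine already has a relative-rise rule.

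The cost is one extra row, a derived flag and a footnote, from data already collected. No case now counted is lost. The drawback is that readers see two definitions side by side, so the labels must keep them apart.

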2.7.4 Other safety data

2.7.4.1 ECG and cardiac imaging data

ECG results will be listed.

2.7.4.2 Vital signs

Observed value, change, and percent change from baseline in vital signs (pulse rate, blood pressure, weight, ██████████) will be summarized descriptively at each analysis visit (including Day 330/Last Visit) by treatment group.

Blood pressure categories will be summarized at each analysis visit (including Day 330/Last Visit) by treatment group. The categories are summarized below. The worst category at an analysis visit will be used in the analysis. A shift table from baseline to each visit will also be created.

Blood Pressure Category	Systolic Blood Pressure (mmHg)		Diastolic Blood Pressure (mmHg)
Normal	<120	and	<80
Elevated	120-129	and	<80
High Blood Pressure Stage 1	130-139	or	80-89
High Blood Pressure Stage 2	140-180	or	90-120
Hypertensive Crisis	>180	or	>120

Reference: [Whelton et al 2017](#).

2.8 Pharmacokinetic endpoints

Not applicable.

2.9 PD and PK/PD analyses

[figure not shown]
Not applicable.

[REDACTED]

2.11 Biomarkers

See [Section 2.6](#).

[REDACTED]

2.13 Interim analysis

After all participants complete their baseline visit, the demographic and baseline characteristics may be summarized to help design new studies. No analysis will be performed using post-baseline data. Thus, there is no need to adjust the level of significance for such interim analysis of baseline data.

3 Sample size calculation

The sample size was calculated for the two primary efficacy variables with adjustment for multiple testing by using the Bonferroni procedure.

For primary efficacy variable 1, i.e., percent change from baseline in LDL-C, the standard deviation is assumed to be 40, partly based on the results from ORION-10 and ORION-11 clinical trials, and considering that the standard deviation will likely be larger in this trial since

changes in lipid-lowering therapy are allowed in both treatment groups. An expected mean treatment difference of 15 is assumed, which is smaller than the mean difference observed in the Phase III trials, to account for 1) potential lower utilization of background lipid-lowering therapy in the "inclisiran first" implementation group compared to the usual care group, and 2) the ability to add non-statin lipid lowering therapy in the usual care group. [REDACTED]

Table 3-1 considers total sample sizes for expected mean treatment differences of 15, 20, and 25 and powers of 0.85 and 0.90 (nQuery Version 8.4.1.0). From Table 3-1, an expected mean treatment difference of 15 at Day 330 and a power of 0.90 were chosen to provide a total sample size of 354 participants.

Table 3-1 Same Size Calculations for Percent Change from Baseline in LDL-C

Mean treatment difference	Power = 0.85	Power = 0.90
15	306	354
20	172	200
25	112	128

For primary efficacy variable 2, i.e., discontinuation of statin therapy (yes, no), a z-test for a non-inferiority test of two proportions, an allocation ratio of 1:1, and a one-sided significance level of 0.0125 were used in the calculation of sample size. Table 3-2 considers total sample sizes for 0.20 and 0.25 as the true proportions of participants who discontinue statin therapy in each treatment group, and non-inferiority margins of 0.10 and 0.15 for the "inclisiran first" implementation group to be no worse than the usual care group (nQuery Version 8.4.1.0). From Table 3-2, a true proportion of 0.20 for participants who discontinue statin therapy in each treatment group by Day 330, a non-inferiority margin of 0.15, and a power of 0.90 were chosen to provide a total sample size of 354 participants.

Table 3-2 Sample Size Calculations for Statin Statin Therapy Discontinuation

Proportion in usual care group	Non-inferiority margin	Power = 0.85	Power = 0.90
0.20	0.10	688	796
0.20	0.15	306	354
0.25	0.10	806	932
0.25	0.15	360	414

Based on the sample size calculations in Table 3-1 and Table 3-2, a total sample size of 354 together with a loss to follow-up rate of 10% at Day 330 and a statin intolerance rate at baseline of 10% (i.e., a total of 20% due to loss to follow-up and statin intolerance at baseline) require

approximately 444 participants (222 participants per treatment group) to be randomized. This will also allow examination of subgroups with reasonable sample sizes.

4 Change to protocol specified analyses

Changes from Protocol version 01 (amended protocol) include the following:

1. Protocol Section 12.4.2 states that an unstructured working correlation matrix will be assumed for the MMRM. An unstructured covariance matrix will be used instead.
2. The protocol uses Day 0 as the first inclisiran dose day. In order to aid in counting of dosing days the first dose day will be referred to as Day 1.

Changes from Protocol version 02 (amended protocol) include the following:

3. Protocol Section 12 notes that the interquartile range will be provided. In order to streamline the tables this statistic was removed.
4. Protocol Section 12.2 notes that relevant medical histories and current medical conditions at baseline would be summarized using the Safety Set, the FAS was used instead.
5. Protocol Section 12.5.1 lists out secondary efficacy variables. The analysis of variable #22 (Intensity of lipid-lowering therapy (decrease in dose, no change in dose, increase in dose) was modified slightly. Intensity of therapy is only available for statins, not for other lipid-lowering therapies used in this study. Therefore, for each participant and analysis visit, the highest statin intensity on each nominal visit date will be compared to baseline statin intensity.
6. Protocol Section 12.5.2 notes that all vital signs and all laboratory data will be listed. In order to streamline the listings, only abnormal vital signs and laboratory data will be provided.

5 Appendix

5.1 Imputation rules

5.1.1 Study drug

Not applicable.

5.1.2 AE date imputation

The following table explains the notation used in the logic matrix. Please note that **missing start dates** will not be imputed.

	Day	Month	Year
Partial Adverse Event Start Date	Not used	MON	YYYY
Treatment Start Date (TRTSTD)	Not used	TRTM	IRTY

[REDACTED]

[REDACTED]

[REDACTED]

[REDACTED]

[REDACTED]

[REDACTED]	[REDACTED]
[REDACTED]	[REDACTED]
[REDACTED]	[REDACTED]
[REDACTED]	[REDACTED]
[REDACTED]	[REDACTED]
[REDACTED]	[REDACTED]
[REDACTED]	[REDACTED]
[REDACTED]	[REDACTED]
[REDACTED]	[REDACTED]
[REDACTED]	[REDACTED]
[REDACTED]	[REDACTED]
[REDACTED]	[REDACTED]
[REDACTED]	[REDACTED]
[REDACTED]	[REDACTED]
[REDACTED]	[REDACTED]
[REDACTED]	[REDACTED]
[REDACTED]	[REDACTED]
[REDACTED]	[REDACTED]

Adverse Event End Date Imputation

- Imputed date = date part of original date, if complete date
- Imputed date = min (completion/discontinuation visit date, DEC 31, date of death), if month is missing
- Imputed date = min (completion/discontinuation visit date, last day of the month, date of death), if day is missing

Imputed Date Flag

- If year of the imputed date is not equal to YYYY then date flag = Y
- Else if month of the imputed date is not equal to MON then date flag = M
- Else if day of the imputed date is not equal to day of original date then date_flag = D
- Else date flag = null

5.1.3 Concomitant medication date imputation

This algorithm is used when *event* is the partial start date of the concomitant medication. The following table explains the notation used in the logic matrix. Please note that **missing start dates** will not be imputed.

	Day	Month	Year
Partial CM Start Date	Not used	MON	YYYY
Treatment Start Date (TRTSDT)	Not used	TRTM	TRTY

[REDACTED]

[REDACTED]

[REDACTED]

Concomitant Medication End Date Imputation

If not ongoing then -

- Imputed date = date part of CMENDTC, if complete date
- Imputed date = min(completion/discontinuation visit date, DEC 31) , if month is missing, (C2, D, E)
- Imputed date = min(completion/discontinuation visit date, last day of the Month) , if day is missing. (A, B, C1)

Concomitant Medication Date Flag

If not a complete date then

- Y - If year of the imputed date is not equal to YYYY
- Else M – If month of the imputed date is not equal to MON
- Else D.

